## 1. Purpose of Study and Background

### 1.1 Purpose

The purpose of EQUIPED is to test and evaluate a care quality improvement intervention featuring use of consensus decisional guidance for the medical management of diabetes (DM) patients with Alzheimer's and other forms of dementia (ADRD) in primary care at NYU Langone Health. This quality improvement program will include provider (PCP) workflow enhancements supported by a panel manager (PM) for workflow support, electronic health record (EHR) decision support and feedback, and PCP collaborative learning.

It will test hypotheses about whether care based on explicit standards for DM medical management for people with ADRD will: **H1**) Improve patient symptoms and quality of life while maintaining expected clinical outcomes; **H2**) decrease patient and caregiver management burden and improve care quality based on patient/caregiver preferences; **H3**) (secondary) decrease specialty, ED and hospital utilization.

In order to test and evaluate this program, we will conduct a pragmatic randomized controlled trial (RCT) and evaluate it using mixed methods (surveys and interviews) in 20 NYU Langone Health clinics with the enrollment goal of 500 patients with diagnosed DM and ADRD in the intervention (INT) and control (CON) group (1,000 total).

If EQUIPED demonstrates that patients and family caregivers who receive this quality improvement program achieve established goals for diabetic care in addition to fewer dementia-related symptoms, less caregiver burden and stress, and fewer DM-related adverse events, potentially avoidable and costly utilization may also decrease. This best practice approach could then be widely disseminated to other clinical practices.

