### 1.2 Specific Aims

Specific Aims of the R33 Enhanced Quality In Primary Care for Elders with Diabetes-ADRD (EQUIPED-ADRD) are:

- 1) Implement and evaluate a pragmatic trial in a large healthcare system using cluster randomization, and the practice change framework, that will: manage people with co-occurring DM and ADRD according to the guidelines developed to test our hypotheses and identify additional patients with cognitive impairment and inappropriate DM management.
- 2) Test whether EQUIPED-ADRD will increase the proportion of intervention patients who are in desirable glycemic and blood pressure ranges compared to control patients.
- 3) Test whether the EQUIPED-ADRD intervention will improve dyad perception of care quality and reduce treatment burden.
- 4) Test whether dementia symptoms will deteriorate less in intervention subjects compared to controls.

**Exploratory Aim.** Test whether intervention subjects will use fewer health care services than controls and will have less cognitive decline associated with desired changes in glycemic and blood pressure control.

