We will train intervention PMs in DM and ADRD management for INT clinics. Training will include one-on-one sessions with the mPI's and co-I's, suggested reading, shadowing relevant clinicians, such as social workers in the Alzheimer's Disease Center and geriatrics clinic, and other relevant activities. We expect training will require one month's duration with subsequent continuous learning activities that include continuing meetings with mPIs and co-I's and travel to national conferences.

**PM Activities.** The PM will reach out to eligible patients with diagnosed DM-ADRD (see section 4.3) and  $\geq 75$  year-old patients with over- and under-treatment of HbA1c/BP for cognitive screening using IQ-CODE as defined in the Guideline. For those with a positive screen, in coordination with the PCP, the PM will facilitate further cognitive evaluation. These patients will become part of the quality improvement intervention. The PM will begin telephonic assessment and DM management education of DM-ADRD patients around the time of the scheduled visit (either just before or just after). The PM will conduct a detailed psychosocial and needs assessment with each willing CG and assess the patient based on both a standardized assessment and clinical judgement. The PM will also engage those CGs who live far from the patient and who manage the patient remotely through paid home health aids (HHA). The CG psychosocial assessment will focus on diabetic management support and family dementia CG support providing referrals as needed to well established New York City programs. The PM will provide PCPs with evaluation data, DM-relevant care suggestions and facilitate PCP visits for care reassessment as clinically appropriate. The PM will assist the PCP and the dyad with developing individualized DM management targets and re-evaluating these targets over time. The PM will maintain dyad follow-ups and monitor patient-level data using EHR follow-up data as per usual clinical care, and an Epic-generated report for relevant issues. The PM will also address dyad goals and treatment preferences and assist with communicating these with the PCP. A key part of PM activity will be determining with each PCP their preferred method of communication (e.g., Epic messaging, order pending, periodic phone calls, etc).

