Consistent PCP care	EHR	% Visits by PCP versus other ambulatory providers	Pt	X	X	X	X

New home health aide or increased hours	Survey	Yes/no; HHA resource changes	Pt	X	X	X	X
New home health care services	Survey	Yes/no	Pt	X	X	X	X
Insurance	EHR	Categorical: Yes/No, Medicare, Medicaid, HMO	Pt	X	X	X	X
DM-ADRD-Specific							
Has a caregiver (Defined: Sec. B5)	EHR	Yes/No	Pt	X	X	X	X
Caregiver living arrangement	Survey	Categorical: Live with subject, close proximity (miles), other	CG	X	X	X	X
Clinic-Specific							
Clinic Size	Admin	Number primary care providers / number of patients	Clinic	X			X
Clinic Support	Admin	Number of clinic support staff / provider	Clinic	X			X
Proportion Medicare/Medicaid	Admin	Insurance data specific to Medicare/Medicaid categories	Clinic	X			X
EQUIPED Process of Care Measures							
Provider use of structured template	EHR	Counts: visit note/templates; proportion of visits with templates	PCP		X	X	X

Provider educational attendance	Admin	Proportion (n, %) of educational sessions attended	PCP		X		
PM – PCP Communication	EHR	Counts: emails, forwarded notes between PM and PCP	PM/PCP		X	X	X
Change in diabetic medication	EHR	Counts: change (add, delete); dosing (increase, decrease)	Pt	X	X	X	X
Change in antihypertensive medication	EHR	Counts: change (add, delete); dosing (increase, decrease)	Pt	X	X	X	X
Medication complexity	EHR	Sum of unique medications, daily dosing frequency/differences	Pt	X	X	X	X
Anticholinergic medication burden	EHR	Anticholinergic medication burden scale	Pt	X	X	X	X
PM – CG contact frequency	EHR	Counts: CG visits with PM (by type: email, phone, in-person)	CG		X	X	X
Referrals for CG-support services	EHR	Proportion (n, %) of CGs referred to programs / receipt of service	CG		X	X	X
Cognitive screening of eligible patients	EHR	Proportion (n, %) of DM-eligible patients screened w/ MiniCog TM39	Pt		X	X	X
Outcome Measures							
General							
Hemoglobin A1C Change	EHR	Proportional change: patients with in-range values versus not	Pt	X	X	X	X

Blood pressure change	EHR	Proportional change: patients with in-range values versus not	Pt	X	X	X	X
Treatment Burden Questionnaire	Survey	15-item survey modified for CG administration (0-10 likert) 	Pt	X	X	X	X
Non-acute care use	ResDAC	Counts: provider ambulatory visits / all health system contacts	Pt	X	X	X	X
Acute care use**	ResDAC	Counts: ED, hospital / #bed days	Pt	X	X	X	X

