We will also measure structure of care variables. These include patient use of consistent PCP care, home health services, and patient insurance. Clinic characteristics are size, support staff number, proportion of Medicare and Medicaid patients. Several baseline variables relate to diabetes but because they are also outcome variables they will be described later. As shown in table 1, many of these baseline and control variables are measured in the EHR and Epic administrative reports, or by claims. Some are measured by validated survey instruments, which are discussed briefly below.

We will collect many process of care measures at baseline and at follow-up. These include: a) provider use of Epic templates and tools; b) provider attendance at educational sessions; c) PM-PCP communication; d) PM-caregiver contact frequency; e) referral for caregiver-support services; f) cognitive screening of diabetes patients over 75; g) change in diabetes medications; h) change in hypertensive medications; i) change in anticholinergic burden; j) change in medication complexity. These variables are measured by EHR review and Epic administrative systems.

Outcome variables include HbA1c level and blood pressure. These variables will be measured at 0, 6, 12 and 24 months when available. Our main outcome is the proportion of patients achieving consensus HbA1c targets. BP will be measured by proportion of patients achieving consensus BP targets per our guideline. These variables will be measured by the EHR.

Utilization outcome variables are ED, hospital, SNF and ambulatory clinic utilization measured by EHR and by claims (for non-New York Langone Health utilization). SNF days must be measured by claims; Epic reports have discharge destination but do not have SNF days. Utilization variables will be measured at 6, 12, 24 months; the baseline measures include a 20 month look back at utilization.

Multiple caregiver reported outcomes about the caregiver and about the patients will also be

collected at 0, 6, 12, 24 months. General outcomes include: a) caregiver perception of care quality (our main caregiver-reported outcome), dyad care goals, preferences, and satisfaction; b) treatment burden; c) caregiver global health. Dementia and diabetes specific outcomes include: a) patient dementia symptoms; b) caregiver diabetes stress.

Below is a brief description of the instruments we will use, all of which have been studied and validated, although not always with caregivers.

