## 7. Data Analysis

We will begin all analyses with descriptive summary statistics and graphical displays of all variables. Continuous variables will be summarized with means, medians, standard deviation and interquartile range; categorical variables will be summarized with frequencies. We will assess the balance by treatment assignment of patients in the INT and CON clinics with respect to demographic and clinical characteristics (e.g., age, gender, Charlson Index, socioeconomic status, baseline TBQ, etc.) using standard tests (t-tests, Wilcoxon rank-sum tests, and  $\chi^2$  tests as appropriate). Any factors that appear to be unbalanced by treatment assignment will be considered as adjustment factors in the primary analyses. All hypothesis testing will be two-sided and conducted using a significance level of 0.05.

The primary outcome of 'on target' HbA1C values will be measured for each patient as a binary indicator. The primary analysis will use a generalized linear mixed model approach, with a logit link, for the probability of being 'on target.' The treatment group (CON vs INT) will be the primary fixed effect of interest; we will also include the practice as a random effect to accommodate clustering of patients within clinics. We will also explore non-parametric methods such as quantile regression or other rank-based approaches. As noted above, randomization should obviate the need for any additional covariate adjustment, but we will explore whether adjustment for clinic-level characteristics (e.g., clinic size) and provider-level characteristics (e.g., provider demographics and panel size) is necessary. We will use standard assessments of goodness-of-fit, including residual plots, to evaluate the models. Finally, in addition to reporting the treatment difference in terms of the odds ratio from the logistic regression, we will report absolute risk difference as well.

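### H3 predicts a fall in specialty use, but no listed outcome or analysis isolates it, and the only ambulatory count mixes specialty visits with visits the intervention helps to arrange

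*Combined protocol and SAP*

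**What the plan says.** Section 1.1 states H3, labelled secondary, as a prediction that the programme will "decrease specialty, ED and hospital utilization". The exploratory aim in section 1.2 is broader: "Test whether intervention subjects will use fewer health care services than controls".

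The outcome block of Table 1 (section 5.4, Measures) has an acute row, "Counts: ED, hospital / #bed days", and a non-acute row, "Counts: provider ambulatory visits / all health system contacts". Both give ResDAC claims as the source. No row counts specialty visits. The text after the table says "Utilization outcome variables are ED, hospital, SNF and ambulatory clinic utilization measured by EHR and by claims", with claims covering use outside the health system. Specialty is not named there either.

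Section 7 gives logistic mixed models for indicators of use and Poisson models for days in facilities. It names no model for visit counts and no split by type of provider.

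Under PM Activities in section 4 (INT Clinics), the panel manager is to "facilitate PCP visits for care reassessment as clinically appropriate", help arrange further cognitive evaluation after a positive screen, and keep up telephone follow-up. Control clinics receive the guideline, an initial patient list and yearly meetings, but no panel manager.

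Two other Table 1 rows matter. One, a structural measure from the EHR, is the percentage of visits made to the PCP rather than to other ambulatory providers. The other, a process measure from the EHR, counts panel manager contacts with caregivers.

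**The concern.** One of H3's three named targets has no outcome of its own. The nearest measure adds specialty visits, which H3 expects to fall, to primary care visits, on which H3 makes no prediction and which the intervention may raise. Cognitive evaluations set up by the programme can enter the same total.

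A total built this way cannot answer the specialty question. A real fall in specialty use could be reported as no difference or as higher ambulatory use. Equally, a fall in the total would not show that specialty visits were the part that fell.

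**Working it through.** **No figure to reproduce.** The documents give no visit rate, effect size, variance, intraclass correlation or power for any utilisation outcome. From the documents I take 500 patients per arm (section 1.1) and the testing rule in section 7: "All hypothesis testing will be two-sided and conducted using a significance level of 0.05". Everything else below is an assumption.

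**Each part of H3 against its outcome**

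| H3 component | Outcome in Table 1 | Isolated? |
|---|---|---|
| ED | Acute care row | Yes |
| Hospital | Acute care row | Yes |
| Specialty | Non-acute row, all ambulatory providers | No |

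This comparison needs no assumed number.

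**When the total misleads.** Let P and S be PCP and specialty visits per control patient-year, b the fractional fall in specialty visits, and a the visits added in the intervention arm. Then

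pooled ratio = [P + a + S(1 − b)] / (P + S),

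which exceeds 1 when a > bS.

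Break-even added visits per year, bS:

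| Assumed S | b = 10% | b = 20% | b = 30% |
|---|---|---|---|
| 3 | 0.3 | 0.6 | 0.9 |
| 6 | 0.6 | 1.2 | 1.8 |
| 8 | 0.8 | 1.6 | 2.4 |

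Pooled ratios with P = 4 and S = 6:

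| Specialty fall | a = 1 | a = 2 |
|---|---|---|
| 10% | (5 + 5.4)/10 = 1.04 | (6 + 5.4)/10 = 1.14 |
| 20% | (5 + 4.8)/10 = 0.98 | (6 + 4.8)/10 = 1.08 |
| 30% | (5 + 4.2)/10 = 0.92 | (6 + 4.2)/10 = 1.02 |

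The direction reverses in four of these six cells. In the other two the fall is diluted.

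**Whether the PCP percentage fills the gap.** With P = 4 and S = 6 the PCP share is 4/10 = 0.40. A 20% specialty fall with no change in PCP visits gives 4/(4 + 4.8) = 0.455. One extra PCP visit with no change in specialty visits gives 5/(5 + 6) = 0.455. The share alone cannot tell the two apart.

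**Rough effect on power.** Take P = 4, S = 6 and a 20% specialty fall (1.2 visits). Assume variance = φ × mean with φ from 2 to 4, intraclass correlation (ICC) from 0.01 to 0.05, and 9 or 10 clinics per arm (section 3.1 supports either number). Effective n per arm = 500 / [1 + (m − 1) × ICC], where m = 500/9 or 500/10, and power = Φ(difference/SE − 1.96).

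- At the unfavourable end (9 clinics, ICC 0.05, φ = 4) the design effect is 1 + 54.6 × 0.05 = 3.73, so effective n = 134.
- Specialty visits alone: power about 0.52 to 0.99.
- Pooled count, no added visits: about 0.34 to 0.94.
- Pooled count, one added visit (net difference 0.2): about 0.04 to 0.08, close to the false-positive rate. The formula counts only rejections in the direction of the fall, which is why it can drop below 0.05.

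**The case against.** The case against has several sound parts.

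- **ED and hospital use.** They are measured separately, so two of H3's three parts are untouched. This stands.
- **Exploratory aim.** A reader might infer that the pooled count also biases the test of fewer services. The documents do not support that. The aim concerns health care services in general, so a total fits it, and extra PCP visits are real services: a rise would be a genuine result against the aim. Replacing that test with ED and hospital use alone would narrow the stated aim.
- **Specialty use is unmeasurable.** This too goes beyond the documents. Table 1 plans to separate PCP from other ambulatory visits, so the information is largely within reach. What is missing is a named outcome and analysis. The planned percentage does not supply them: it is a structural measure, comes from the EHR while the outcome row comes from claims, and providers other than the PCP need not be specialists.
- **Panel manager calls inflate the count.** This is unproven. The outcome row is patient-level and claims-based, and panel manager contacts have their own caregiver-level row. But the text also draws utilisation from the EHR, and the reference to all health system contacts is undefined, so a definition is needed. No effect should be calculated from it.
- **The slash.** It may separate two counts, as it seems to in the acute row. Even so, the provider-visit count would still combine primary and specialty care.
- **Size of the added visits.** The panel manager works largely around visits already scheduled and facilitates others only as clinically appropriate. Further cognitive evaluation follows a positive screen, and control patients with a low score should also be assessed further. One or two extra visits for every intervention patient is not documented, so a reversal is possible but not established.

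**Conclusion.** The concern holds for the specialty part of H3. The hypothesis is stated, but no listed outcome or planned analysis isolates it, and the only ambulatory measure includes visits the intervention arm is helped to make. That gap rests on the text alone.

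Its numerical effect rests on assumed visit rates. At 6 specialty visits per patient-year, 0.6 to 1.8 added visits cancel a 10% to 30% fall; over 3 to 8 specialty visits the range is 0.3 to 2.4. Below break-even the total still falls, but by less than specialty use does. The power figures depend further on the assumed dispersion and intraclass correlation and show scale only.

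The point concerns one component of a secondary hypothesis. It does not touch the primary HbA1c outcome, the ED and hospital parts of H3, or the exploratory aim. It is still worth correcting, because the remedy is cheap and without it the trial cannot answer a question it has set itself.

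**What to change.** In Table 1 and the utilisation paragraph of section 5.4:

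1. Add specialty visits as the named ambulatory outcome for H3, defined by provider specialty in the EHR and claims extracts, with the source for each setting stated.
2. Report primary care visits separately, with no predicted decrease, and show cognitive-evaluation visits prompted by the programme on their own line.
3. Keep the total ambulatory count for the exploratory aim.
4. Define what counts as a health system contact, say whether the slash separates two counts, and state that panel manager contacts, already a process measure, are not included.

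In section 7, name a count model for visits, with practice as a random effect as in the other models.

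No new data collection is needed. The cost is coding provider specialty in both extracts. Section 5.4 has claims being applied for in the second or third year under an IRB modification, so the definition can be settled before that request.

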### **INT Clinics:**

In the INT clinics we will introduce the panel manager (PM) to all clinic staff and develop processes for interaction. The PM will work with INT clinic providers to individualize communication methods between the PCP and PM. Each month INT clinic providers will get a list of eligible patients who have appointments with them in the coming month - those with diagnoses of DM-ADRD and those 75 and older with DM who are out of range for HbA1c or BP. This process gives providers monthly reminders about the ongoing quality improvement study and is a more intensive form of QI intervention than provided to CON clinics.

Because this is a pragmatic trial, the clinical team and a project-funded PM will deliver the intervention, fitting it as closely as possible into usual clinical workflow. The clinical team includes PCPs, occasional APNs and PAs (who function as PCPs), RN's, MA's, office staff, and clinic onsite administration. The PM will be part of the team; PMs providing chronic disease self-management support (usually telephonic) are clinic team members in many healthcare systems.

We will assign two PMs to 9 randomly selected INT clinics. Each PM will have 4.5 INT clinics and will engage and focus on their first clinics in a randomly ordered step-wise fashion working within 1-2 clinics over a focused 3-month period before moving on to the next 1-2 clinics for 3 months, then the last 1-2 clinics for 3 months. Our preliminary data suggests 20-50 patients per INT clinic with DM-ADRD  $\geq 65$  years; and about an equal number with DM without ADRD who will screen positive for cognitive impairment, most of whom are  $\geq 75$  years and identified by HbA1c/BP over or under treatment, or identified by provider referral, which we will allow. With 9 INT clinics, given our preliminary data about patient numbers, each PM will have an anticipated 300 dyads. PMs can engage about 33 patients/month, making initial 300 patient/CG contact in 9 months.

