### **6.3 Potential Benefit to Subjects**

We anticipate that participants may receive benefit either from enhanced panel management or usual care and for all we anticipate some immediate benefit regardless of the arm into which they are randomized. All subjects will be recipients of care in clinics that have received guidelines for enhanced care and will be offered referral information for caregiver support services and other informational materials. Contact from an RA may be a break from what for some will be the loneliness of caregiving. We expect some improved caregiver knowledge, decreased sense of burden and improvement in mood for at least intervention subjects. Care recipients may benefit through improved health outcomes. They may also receive increased medical care quality through attention to previously unattended medical issues. Finally, both caregivers and care recipients may receive increased levels of community support through mobilized informal supports and through community agency assistance. This study poses minimal risk to subjects, since the study does not involve tests or treatments beyond that which they would normally receive as part of their normal care. Therefore, the potential benefits outlined above exceed the risks of participation in the study.

For PCPs and staff, participation in interviews poses minimal risk. The opportunity to contribute to better understanding about health service delivery may provide some personal satisfaction and benefit. Information gathered from these interviews may lead to an improved work environment providing direct benefit to participants and colleagues. The interview may also be a place where

PCPs and staff feel free to voice concerns or objections to clinical approaches and this may present a safe space in which to do this.

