All clinical trials are at risk for missing data. Although we will attempt to retain as high a fraction of participants as possible, we acknowledge that some attrition is likely, leading to missing outcome values. The generalized linear mixed models proposed for the primary and secondary analyses incorporate an assumption of data that are missing at random (MAR), meaning that the likelihood of a value being missing depends on observable characteristics (e.g., sex, age, baseline clinical status, etc). In sensitivity analyses, we will assess the impact of different assumptions about the missing data mechanism, and will determine the robustness of trial results to these different assumptions. These sensitivity analyses will take the several forms. The first extreme value imputation, in which we assume that all members of one intervention group experience either a success or a failure (e.g., HbA1 on or off target) while the opposite occurs in the other intervention group. We will also apply a more formalized assessment using the Index of Sensitivity to Nonignorability, developed by [name] and colleagues, which provides an objective assessment of the robustness of trial results to different assumptions about the missing data mechanism.

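### HbA1c and BP count only if routine care produced a result, and the plan does not report or model who gets tested, so the primary comparison can be biased in either direction

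*Combined protocol and SAP*

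**What the plan says.** **Outcome and source.** Section 5.4 (Measures) states: "Our main outcome is the proportion of patients achieving consensus HbA1c targets". BP is handled the same way. On source and timing it says "These variables will be measured by the EHR" and "These variables will be measured at 0, 6, 12 and 24 months when available". Section 6.3 says that "the study does not involve tests or treatments beyond that which they would normally receive as part of their normal care". No measurement window is given, nor a rule for a patient with several values or none.

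**What differs by arm.** In Section 4 (INT Clinics) the panel manager will "facilitate PCP visits for care reassessment as clinically appropriate". The same section adds: "The PM will maintain dyad follow-ups and monitor patient-level data using EHR follow-up data". INT providers also receive monthly lists, which the protocol says "is a more intensive form of QI intervention than provided to CON clinics", and twice-yearly reports that include the proportions in range. CON clinics receive a list at the start and a yearly visit from the investigators.

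**Missing data and model.** In Section 7 the plan says "we acknowledge that some attrition is likely, leading to missing outcome values". It assumes missing at random, with missingness depending on observable features such as sex, age and baseline clinical status. The primary model is a logistic mixed model with treatment as the fixed effect and practice as a random effect. Unbalanced factors will be considered for adjustment, and clinic-level and provider-level covariates explored. Two sensitivity analyses follow: extreme-value imputation in opposite directions by arm, and the Index of Sensitivity to Nonignorability (ISNI).

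**The concern.** Because the study orders no tests, a fully retained patient has no HbA1c at a wave unless routine care produced one. That is a route to missing outcomes separate from dropout, and Section 7 does not name it. It is foreseeable here: Section 1.3 reports that patients with both conditions have poorer diabetes monitoring. It may also differ by arm, since only INT has a person whose work includes bringing patients back to the PCP and following them up.

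The stated missing-at-random assumption and the stated model do not match. The assumption lets missingness depend on baseline clinical status. The firm model terms are treatment and practice only, and baseline HbA1c is not named among the possible adjusters. As written, the primary estimate is unbiased only if having a result is unrelated to on-target status within arm and practice, or related to it in the same way in both arms. If neither holds, the trial could report a difference in glycaemic control that is really a difference in who was tested, or could hide a real one.

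**Working it through.** **Inputs from the documents:** 500 patients per arm (Section 1.1); two-sided 0.05 (Section 7); 9 INT and 9 CON clinics (Section 3.1, which also speaks of 20 practices; 18 is used here). The documents give no on-target rate, effect size, intraclass correlation (ICC) or expected share with a result, so there is no stated figure to reproduce.

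**Assumed inputs:** true on-target rate p = 50% in both arms (no treatment effect), and the testing rates in the table.

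**Formula.** Let m_on and m_off be the chances of having a result when on and off target. Then

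observed rate = p·m_on / [p·m_on + (1 − p)·m_off].

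Equivalently, observed odds = true odds × (m_on / m_off). With no true effect, the spurious odds ratio is (m_on/m_off in INT) ÷ (m_on/m_off in CON).

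| INT tested, on/off target | CON tested, on/off target | Observed INT | Observed CON | Difference (points) | Odds ratio |
|---|---|---|---|---|---|
| 90% / 90% | 75% / 75% | 50.0% | 50.0% | 0 | 1.00 |
| 85% / 85% | 60% / 80% | 50.0% | 0.30/0.70 = 42.9% | +7.1 | 1.33 |
| 85% / 85% | 70% / 80% | 50.0% | 0.35/0.75 = 46.7% | +3.3 | 1.14 |
| 85% / 85% | 80% / 60% | 50.0% | 0.40/0.70 = 57.1% | −7.1 | 0.75 |
| 90% / 90% | 65% / 85% | 50.0% | 0.325/0.75 = 43.3% | +6.7 | 1.31 |

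Row 1 shows that a different share tested does not by itself bias the comparison. Rows 2 to 5 show that bias appears once testing depends on status in one arm and not the other. Putting the 60%/80% pattern in INT, with flat testing in CON, also gives −7.1 points. For true rates of 40% and 60%, row 2 becomes +6.7 and +7.1 points.

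**Effect on the test (row 5).** Patients with a result: 500 × 0.90 = 450 and 500 × 0.75 = 375. SE = √(0.5·0.5/450 + 0.433·0.567/375) = 0.0348, so z = 0.0667/0.0348 = 1.92 and the chance of rejection is 48% without clustering. With design effect 1 + (m − 1)·ICC and m = 825/18 = 45.8, it is 36%, 28.5% and 19% at ICC 0.01, 0.02 and 0.05. The nominal level is 5%.

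**What the planned extreme-value check shows (row 2).** As shares of all enrolled, INT has 42.5% observed on target and 15% missing; CON has 30% and 30%.

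- Lower bound: 42.5 − (30 + 30) = −17.5 points.
- Upper bound: (42.5 + 15) − 30 = +27.5 points.

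Even an observed gain from 50% to 60% with only 10% missing per arm gives 54 − (45 + 10) = −1 to (54 + 10) − 45 = +19 points.

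**The case against.** The strongest defence is that Section 7 already covers this. Its sensitivity analyses are not limited to dropouts. Extreme-value imputation runs in opposite directions by arm, and ISNI is aimed at nonignorable missingness. In the row 2 example the bounds would mark the spurious 7.1 points as not robust. This stands: a reader might infer that the plan does nothing about such missingness, and that is not so. What remains is that bounds this wide would also call most real effects non-robust, and neither check tells the reader whether testing differed by arm.

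A second defence is that the arms differ less than the concern suggests. Both get the guideline, PCP training, EHR tools, basic feedback and encouragement to set and revisit individual targets. The INT monthly lists cover patients who already have appointments, and no section expressly tasks the panel manager with prompting HbA1c tests. This stands too, as a limit on how large the effect may be. It does not remove the panel manager's role in visits and follow-up.

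Third, a reader might infer that the bias favours the intervention because INT testing would be close to universal. The documents do not support that. The panel manager chooses whom to engage on clinical grounds, may prioritise a patient with poor BP control, and facilitates visits by clinical judgement. INT testing could therefore itself depend on status, which can push the bias against the intervention.

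Finally, Section 7 does leave room for covariates. They are possibilities, not commitments, and no predictor of HbA1c testing is named.

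**Conclusion.** The point holds in this form: availability of a routine result is a separate cause of missing primary outcomes. The intervention can plausibly influence it, and the plan neither measures it by arm nor conditions on its predictors in the stated primary model. The generic sensitivity analyses bound the problem but cannot separate a testing difference from a glycaemic one.

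Under the assumed rates the spurious difference is about 3 to 7 points in either direction (odds ratio 1.14 to 1.33, or 0.75 when the 60%/80% pattern is reversed). It is zero if testing is unrelated to status. Every testing rate, the 50% on-target rate and the ICCs are assumptions. No figures were worked for BP, though the same formula applies. The documents do not show that such bias will occur or which way it would run; they show that the trial as planned could not tell. It is a change worth making because it needs only data already in the EHR.

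**What to change.** In Section 5.4 and Section 7:

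1. **Windows and value selection.** Extract all dated HbA1c and BP values. Apply the same non-overlapping windows and the same value-selection rule in both arms, for example 3 to <9, 9 to <15 and 18 to 24 months. Anchor baseline on a date defined identically in both arms, not on panel-manager contact, which CON patients do not have.
2. **Testing by arm.** Report whether an HbA1c result exists in the window (yes/no) by arm, using the same mixed model, next to the primary result.
3. **One added analysis.** Pre-specify an analysis that conditions on, or weights by, predictors of testing fixed before the intervention starts: baseline HbA1c status (with a category for missing), prior-year testing and visit counts, age, sex and comorbidity, fitted within arm. Visit counts after the intervention starts should not be used, because the intervention can change them. Keep the extreme-value and ISNI analyses, and state that the added analysis still assumes missing at random given these covariates.

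Cost: an EHR query and SAP wording, with no added tests, visits or patient burden. The downside is some lost precision in the added analysis and unused values outside the windows (months 15 to 18 in the example).
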